There is a robust literature that demonstrates that adequate consumption of omega 3 (or n-) polyunsaturated fatty acids (PUFA) derived from marine fish, specifically eicosapentaenoic acid (EPA) and docosahexaenoic acid (DHA), is important for maintaining health across the life course. For example, EPA+DHA status¹ and dietary intake² have been shown consistently to improve cardiovascular health and pharmaceutical preparations of these fatty acids have been demonstrated in meta-analyses to be as effective as statins in preventing myocardial infarction³. Anti-inflammatory effects of increased EPA+DHA intake include consistent improvement across studies in the severity of rheumatoid arthritis⁴ and there are emerging findings that support beneficial effects in asthma and inflammatory bowel disease⁵. The recommended daily intakes vary between 250 mg/day (European Food Safety Authority⁶ to 1000 mg/day (Japanese Ministry of Health⁷) of EPA+DHA. In the UK, the Scientific Advisory Committee on Nutrition (SACN 2004) has recommended that adults should consume at least 450 mg/day of EPA+DHA⁸. UK adults consume approximately 50% of the amount of EPA+DHA that is recommended to promote health, while intakes in children are about 10% of that in adults⁹. This is consumed in oily fish or fish oil containing supplements. The low intake of EPA+DHA may be as a result of issues such as the palatability or the cost of consuming oily fish and fish oil. To increase the intake of oily fish and fish oil in the population would be challenging and would also increase the pressure on fish stocks. Algal oils that contain DHA or EPA+DHA have also been proposed as an alternative source of these fatty acids¹⁰ and these currently account for 2% of human EPA+DHA consumption¹¹. However, the current costs of fermentation and refining processes are substantially greater than for FO production and are unlikely to decrease in the medium term¹². Therefore there is a need for an alternative cost effective sustainable source of EPA+DHA.

Vegetable oils derived from genetically modified plants represent a potentially attractive alternative means of providing EPA+DHA for the human population. Such oils potentially overcome issues of the palatability, sustainability and also concerns about contamination of FO with marine pollutants¹³. Insertion of desaturase and elongase enzymes from yeast and algae into the model plant *Arabidopsis thaliana* produced an oil containing 12-15% DHA (but little EPA), which could produce per hectare sufficient DHA to replace 10,000 oily fish¹⁴. It is important to note that most standard FO preparations contain ~18% EPA and ~12% DHA. The health benefits derived from FO are due to both EPA and DHA, and thus plant oils containing only one or the other of these PUFA may have limited effectiveness in supporting optimal health. *Camelina sativa* is a seed oil plant which was the most important seed oil crop in Europe up until the last century. *Camelina sativa* plants have been modified by the addition of genes from other plant sources to be able to provide seed oil with around 10% EPA and 10% DHA. This oil from genetically modified *Camelina sativa* (high omega 3 Camelina oil) is an alternative dietary source of these fatty acids usually found in fish oil and oily fish. The high omega 3 Camelina oil does not represent the synthesis of an entirely new compound, but is a “blend” of the fatty acids found in either vegetable or fish oil. This high omega 3 Camelina oil offers a final possible advantage over conventional fish oil. Fatty acids can be attached to the carrier molecule (triglyceride) in one of three positions (named sn-1, sn-2 and sn-3). The fatty acids are removed from the carrier molecule by enzymes, which release them to be used within the body. These enzymes are better able to remove fatty acids at the sn-1 and sn-3 position and less efficient at removing them from the sn-2 position. In fish oil almost all of the DHA and nearly half of the EPA is attached at the sn-2 position¹⁵. In the high omega 3 Camelina oil, EPA and DHA are attached predominately at the sn-1 and sn-3 positions suggesting the possibility that EPA+DHA in the high omega 3 Camelina oil is more easily released for use by the body.

Therefore, high omega 3 Camelina oil offers a sustainable, cost-efficient source of EPA+DHA. Compared with the current major source of EPA+DHA (fish oil), it avoids issues of contamination with marine pollutants and pressure on fish stocks. Finally it offers the possibility of being more efficacious compared with fish oils due to the way it carries the EPA+DHA.

This study will measure the effectiveness of high omega 3 Camelina oil compared with equivalent fish oil (similar EPA+DHA content) to:

- Increase the body EPA+DHA status in the short and longer term.
- Exert anti-inflammatory and immunomodulatory influences.

8. Aims & Objectives

The overall aim is to test whether the efficacy of dietary high omega 3 Camelina oil is comparable with fish oil for the following:

- The magnitude of the increase and turnover of EPA+DHA in plasma lipids following acute consumption (postprandial period).
- The magnitude of the increase in EPA+DHA derived in plasma lipids and blood cells following consumption over a longer period (provided as a dietary supplement for 8 weeks).
- In vivo and ex vivo anti-inflammatory effects following acute and longer duration consumption.

Objectives

- To measure the appearance of EPA and DHA in individual blood lipid classes (phospholipids, triacylglycerol (TAG), non-esterified fatty acids (NEFA) and cholesteryl esters (CE)) and specific lipoprotein fractions (chylomicrons and very low density lipoprotein) and blood cells (erythrocytes and peripheral blood mononuclear cells) in the blood of healthy subjects over 8 hours following consumption of a standard high fat meal containing high omega 3 Camelina oil compared with consuming the same meal containing an equivalent fish oil (similar EPA+DHA content). (Study A)
- To measure the appearance of inflammatory mediators (including CCL2/MCP-1, CCL4/MIP-1 beta, CRP, IL-1beta, IL-6, IL-8, IL-10, IL-12p70, sICAM-1, Serpin E1/PAI-1, sVCAM-1, TNF-alpha and VEGF and CRP) in the blood of healthy subjects over 8 hours following consumption of a standard high fat meal containing high omega 3 Camelina oil compared with consuming the same meal containing an equivalent fish oil (similar EPA+DHA content). (Study A).

3. To measure the concentration of EPA and DHA in individual blood lipid classes (phospholipids, triacylglycerol (TAG), non-esterified fatty acids (NEFA) and cholesteryl esters (CE)) and blood cells (erythrocytes and peripheral blood mononuclear cells) in the blood of fasted healthy subjects following consumption of high omega 3 Camelina oil for 8 weeks compared with consuming an equivalent fish oil (similar EPA+DHA content) for the same time period. (Study B).
4. To measure in vitro immune responses (mononuclear cell mediator production, mononuclear cell and neutrophil phagocytosis and respiratory burst response, T cell signalling) by cells from the blood of fasted healthy subjects following consumption of high omega 3 Camelina oil for 8 weeks compared with consuming an equivalent fish oil (similar EPA+DHA content) for the same time period. (Study B).

9. The study

Subjects

For each study (A and B) we will recruit to enrol 10 healthy men and 10 healthy women each in two age ranges (18 to 30 years or 50 to 65 years). We estimate (based on past experience) that this will require screening of approximately 30 men and 30 women in each age group for each study⁵⁵.

For the purpose of this study healthy will be defined as having health screening results that are within normal ranges, a body mass index of 18.5-30.0 kg/m² and without diagnosis of chronic illness.

Inclusion criteria

1. Male or female
2. 18 to 30 years or 50 to 65 years
3. Body mass index 18.5-30.0 kg/m²
4. Health screening results that are within normal clinical ranges (systolic blood pressure ≤ 140 mm/Hg, diastolic blood pressure ≤ 90 mm/Hg, total cholesterol concentration < 7.5 mmol/L, random glucose concentration < 11 mmol/L)
5. Not consuming fish oil or other oil supplements
6. Not eating more than one oily fish meal per week
7. Willing to adhere to the study protocol
8. Being able to provide written informed consent

Exclusion criteria

1. Aged < 18 years; 31-49 years or > 65 years
2. Body mass index < 18.5 or > 30 kg/m²
3. Current smoker
4. Random sample blood cholesterol or glucose concentrations outside the normal concentration range
5. Diagnosed chronic illness (for example diagnosed cardiovascular disease, diabetes, cancer, rheumatoid arthritis)
6. Diagnosed food allergy.
7. Regular use of anti-inflammatory medication (e.g. aspirin, ibuprofen, diclofenac) or anti-coagulant therapy.
8. Use of prescribed medication to control blood lipids (e.g. statins, fibrates (fenofibrate), Omacor, bile acid resins) or fat absorption (e.g. orlistat)
9. Use of prescribed medication to control blood pressure (ACE inhibitors, angiotensin 2 receptor blockers, calcium channel blockers, α-inhibitors, thiazide diuretics)Use of fish oil or other oil supplements
10. Chronic gastrointestinal problems (e.g. IBD, celiac disease, cancer)
11. Pregnant or planning to become pregnant within the study period
12. Participation in another clinical trial

Medications which are not incompatible with the study and are thus acceptable include contraceptives, hormone replacement therapy, antacids, anti-depressants, inhaled steroids or beta-agonists for

asthma, topical steroids or other nasal sprays for seasonal or perennial rhinitis, thyroxine. Certain stable, managed, chronic conditions do not constitute an exclusion (e.g. asthma, seasonal or perennial rhinitis, hypothyroidism).

Subjects will be recruited via posters, intranet and email shots in the University of Southampton, via posters, and email shots in Southampton General Hospital, and other organisations with which the researchers have contact; and via advertisements in local media including newspapers and radio. Subjects who express an interest will be contacted by telephone or email. If they fit the inclusion and exclusion criteria (see below) they will be sent the information sheet. They will be contacted about 7 days later to confirm their interest or not, and if they remain interested an appointment will be made for them to visit the Wellcome Trust Clinical Research Facility at Southampton General Hospital. At this first visit the study will be explained, any questions answered and written consent obtained.

Supplements

The fish oil n-3 fatty acid preparation to be used is commercially available as a supplement and will be provided incorporated into the high fat meal for study A and as a dietary supplement oil for study B. The Camelina oil is an edible plant seed oil but additionally will contain the fish oil-type fatty acids EPA plus DHA. Approximately 450 mg EPA plus DHA will be provided by the oils (fish oil or high omega 3 Camelina oil) for the meal challenge (study A). For study B the oils (fish oil or high omega 3 Camelina oil) will provide 450 mg EPA plus DHA per day for the 8 weeks of the intervention period (providing the recommended UK daily intake)¹⁷.

The high omega 3 Camelina oil contains around 10% of fatty acids as EPA and 10% as DHA. It will be given incorporated into the high fat meal for study A and as dietary supplement oil for study B. Subjects will be randomised to allocate order of supplement. Subjects, researchers and clinical staff will be blinded to group allocation.

Subject participation schedule

Study A

Subjects who express an interest will be contacted by telephone or email. If they fit the inclusion and exclusion criteria they will be sent the information sheet. They will be contacted about 7 days later to confirm their interest or not. If they remain interested an appointment will be made for them to visit the NIHR Wellcome Trust Clinical Research Facility, Southampton General Hospital. At this first visit the study will be explained, any questions answered and written consent obtained; subjects will then have height, weight, and blood pressure measured and a screening blood sample collected (10 ml) to confirm that they meet the inclusion criteria. An appointment will be made for the subsequent clinic visit; one further clinic visit will be made (i.e. three clinic visits in total). Subjects will attend the 2 latter clinic visits in the fasted state (no food or drink except water after 8 pm the previous evening).

Subjects will visit the Wellcome Trust Clinical Research Facility, Southampton General Hospital on three occasions.

[figure not shown]
At the second and third visits the subjects will attend the clinic between 7 and 9 am and will have a cannula inserted into a forearm vein and a baseline blood sample (10 ml) collected. Subjects will then consume one of the test meals on each of two study visits in random order.

The composition of the test meals will be based upon typical UK nutrient intakes as we have used in previous post-prandial studies. The lipid component will be derived from a blend of fat sources (fish oil or high omega 3 Camelina oil, safflower oil, double cream, linseed oil and olive oil) to model the fatty acid profile of the UK diet. Approximately 450 mg EPA plus DHA will be provided by the oils (fish oil or high omega 3 Camelina oil) for the meal challenge (providing the recommended UK daily intake)¹⁷.

Blood samples (10 ml) will then be collected for 8 hours (at 30 minute intervals up to 3 hours and then hourly; total volume sampled 120 ml). A light meal (e.g. sandwiches) will be provided at the end of

the visit. Subjects will then consume the other test meal at the next study visit which will be at least 14 days after the first. This will complete study A.

Study A

Study B

[figure not shown]
Subjects who express an interest will be contacted by telephone or email. If they fit the inclusion and exclusion criteria they will be sent the information sheet. They will be contacted about 7 days later to confirm their interest or not. If they remain interested an appointment will be made for them to visit the NIHR Wellcome Trust Clinical Research Facility, Southampton General Hospital. At this first visit the study will be explained, any questions answered and written consent obtained; subjects will then have height, weight, and blood pressure measured and a screening blood sample (10 ml) to confirm that they meet the inclusion criteria.

Subsequently four further clinic visits will be made. Subjects will attend each of these four clinic visits in the fasted state (no food or drink except water after 9 pm the previous evening).

Subjects will visit the NIHR Wellcome Trust Clinical Research Facility, Southampton General Hospital on five occasions the first to obtain consent and collect a screening blood sample, then to attend four study appointments, each between 8 and 11 am. On each occasion following the first visit they will be in the fasted state.

At the four subsequent study visits the subjects a blood sample (40 ml) will be collected. The first of these visits will be a baseline visit and the subject will receive either the fish oil or high omega 3 Camelina oil supplement (allocated by randomisation). The subject will return for the second study visit after consuming the supplement for 8 weeks. At study visit 2 a blood sample will be collected and the subject will commence the 6 week wash out period. After this period they will return for study visit 3 where a blood sample will be collected (as verification that the subject's blood fatty acid composition has returned to the values seen pre-supplementation) and the subject given the second supplement. The subject will consume this daily for 8 weeks and then return for study visit 4. This will complete study B.

Study B

Schedule of subject visits and activities performed at each visit

X indicates the activity will take place.

Visits 1 and 2 and 3 to 4 will be around 8 weeks apart and subjects will consume fish oil or high omega 3 Camelina oil daily during that period. Visits 2 to 3 will be a 6 week wash-out period.

Activity	Screening Visit	Study Visit 1	Study Visit 2	Study Visit 3	Study Visit 4
Subject fasted		X	X	X	X
Informed consent	X				
Height	X				
Weight	X	X	X	X	X
Blood for screening	X				
Blood for fatty acids, and in vitro immune and inflammatory responses		X	X	X	X

Sample analysis

Blood collected at study entry will be used for screening. This will be analysed by the University Hospital Southampton NHS Foundation Trust Chemical Pathology Laboratory for blood cholesterol and blood glucose.

Study A. At the 2 study visits blood will be used to prepare plasma, mononuclear cells and red cells. Plasma will be aliquoted and frozen at minus 80°C. Mononuclear cells and red cells will be frozen at minus 80°C. Lipid will be extracted from plasma and red cells using chloroform/methanol and fatty

acid composition determined using standard techniques. Size distribution and concentration of chylomicron, VLDL, LDL and HDL lipoprotein particles will be analysed by NMR in samples collected at baseline, 3 and 8 hours. Immune and inflammatory mediators will be measured in plasma using multiplex immunoassays.

Study B. At the 4 study visits blood will be used to prepare plasma, mononuclear cells and red cells. Plasma will be aliquoted and frozen at minus 80°C. Mononuclear cells and red cells will be frozen at minus 80°C. Lipid will be extracted from plasma and red cells using chloroform/methanol and fatty acid composition determined using standard techniques.

Plasma will be used to evaluate blood lipid concentration and particle sizes

Mononuclear cells will be cultured for 24-48 hours and immune mediators in response to stimulation measured in plasma will be measured using multiplex immunoassays and ELISA.

Whole blood will be used to investigate neutrophil phagocytosis and respiratory burst response to bacterial challenge. Whole blood will be used to measure mononuclear cell phagocytosis.

T cells from the mononuclear cells will be mitogen stimulated and the RNA harvested in prepared for microarray analysis of the T cell transcription.

Data will be compared across time and between groups by ANOVA with repeated measures.

10. Data handling and record keeping

- All data will be entered onto a spreadsheet (Microsoft Excel) by the researchers involved.
- All data will be entered on a password-protected computer. This data will be accessed only by the PI and the researchers involved.
- All data will only be linked to study codes and thus not identifiable with the source volunteer. However, the caveat to this will be a data set recording the volunteer name and study code without any other volunteer details.
- All data recorded on paper will be kept in a locked filing cabinet in the researchers' office and/or in a dedicated, restricted access, clinical data storage area on Level D of the IDS Building, University of Southampton.
- Data of an identifiable nature (i.e. volunteer names, contact details, addresses) will be destroyed 12 months after the end of the study. All other data will be kept securely for 15 years and then destroyed.
- Data will be obtained, handled and stored in adherence to the principle set out in the Data Protection Act 1998.
- The investigators will permit monitoring, audits, REC and MHRA review (as applicable) and provide direct access to source data and documents.

11. Statistical Analysis

The statistical analysis will involve the comparison of inflammatory markers (proteins, lipids etc) and of fatty acids between fish oil and High omega 3 Camelina oil supplements. All statistical comparisons will be performed at the end of the study using SPSS version 21 (or later).

12. Sample size calculation

Study A. Based on our published findings¹⁶, ten subjects per group will provide 85% power for detecting a 10% difference in peak postprandial concentrations of EPA or DHA in plasma TAG at $\alpha = 5\%$ and $\beta = 7.5\%$ in a two tailed analysis. Based on our previous findings of the effect of consuming a FO-enriched meal on lipoprotein size and concentration¹⁷, Ten subjects per group will provide 85% power for detecting 13 nmol/l difference in peak postprandial VLDL concentration and 11 nm difference in VLDL particle size ($\alpha = 5\%$ and $\beta = 7.5\%$) in a two tailed analysis. Based on our preliminary data, ten subjects per group will provide 80% power for detecting a maximum change of 0.8pg/ml IL-6 (30% difference) in a two-tailed test ($\alpha = 5\%$ and $\beta = 20\%$).

Study B. Based upon our previous work¹⁸, ten subjects per group will provide 80% power for detecting a 40% increase in EPA or DHA in plasma phospholipids ($\alpha = 5\%$ and $\beta = 7.5\%$) in a two tailed test based upon after 30 days supplementation. Based upon our previous work¹⁹, ten subjects per group will provide 85% power for detecting a 10% increase in concanavalin A stimulated IL-4 and IL-2 secretion in vitro ($\alpha = 5\%$ and $\beta = 7.5\%$) in a two tailed test based upon after 30 days supplementation. In the first instance, data from the two phases of the cross over studies will be compared for time effects and if no significant time effects are detected, the data sets for each treatment will be combined¹⁸. Non-parametric data will be normalised by log transformation. The postprandial changes in plasma metabolites will be analysed by ANOVA with treatment, age and sex as fixed factors and time as a repeated measure. The effect of the different oils on plasma metabolites and immune function in the dietary supplementation study will be assessed by ANCOVA with baseline as a covariate.

13. Safety assessments

The supplements are edible oils (fish oil and Camelina oil) which are already consumed in the human diet and have been for many hundreds of years. The Camelina oil will be produced from the seed of the seed oil crop plant *Camelina sativa* which has been genetically modified by inclusion of genes from other plant sources which enable this seed oil plant to make fish oil-type fatty acids (long-chain omega 3 fatty acids). Oils produced from GM plants have been produced and are used for human consumption in a number of countries including the United States and Canada. The use of genetic modification to improve the nutritional characteristics of the types of fatty acids within the oil seed crops has been achieved successfully in other seed crops and has been approved for food use by Health Canada and the European Food Safety Authority^{1,2,3}. Genetically modified soybean which produces oil with a much higher oleic acid content (considered to be a healthier fatty acid) has been approved for import and processing for food use in the UK⁴. *Camelina sativa*, a member of the cabbage family (*Brassicaceae*) and related to mustard, is a traditional food plant which has been used in the human diet for thousands of years⁵. It was the most important seed oil crop in Europe up until the nineteen hundreds³. In the USA and Canada it has been cultivated and used as a biofuel^{6,7,8}. More recently, cold-pressed *Camelina sativa* oil has been approved as a food ingredient in Canada⁹. It is naturally rich in the shorter chain omega 3 fatty acid alpha-linolenic acid, and has been used in human intervention studies and reported to reduce LDL cholesterol in hypercholesterolaemic subjects¹⁰. The oil produced from the genetically modified *Camelina sativa* will contain more of the long-chain omega 3 fatty acids which are normally consumed in fish oils or oily fish.

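### The aim is to test whether Camelina oil is comparable with fish oil, but the plan has no limit or interval rule for comparable, and Study B's power statements name no comparator

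*Combined protocol and SAP*

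**What the plan says.** **Aim.** Section 8: "The overall aim is to test whether the efficacy of dietary high omega 3 Camelina oil is comparable with fish oil". This covers acute and 8-week EPA+DHA responses and anti-inflammatory effects. The objectives beneath it are worded as measuring outcomes on one oil compared with the other. The background also raises, as a possibility, that Camelina oil may be more efficacious.

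**Analysis.**
- Section 9, end of Sample analysis: "Data will be compared across time and between groups by ANOVA with repeated measures".
- Section 11: "The statistical analysis will involve the comparison of inflammatory markers (proteins, lipids etc) and of fatty acids between fish oil" and Camelina oil.
- Section 12, Study A: postprandial changes "will be analysed by ANOVA with treatment, age and sex as fixed factors and time as a repeated measure".
- Section 12, Study B: the effect of the oils "in the dietary supplementation study will be assessed by ANCOVA with baseline as a covariate". The two crossover phases are combined only if no significant time effect is found.

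**Study B power (section 12).** "ten subjects per group will provide 80% power for detecting a 40% increase in EPA or DHA in plasma phospholipids", and "ten subjects per group will provide 85% power for detecting a 10% increase in concanavalin A stimulated IL-4 and IL-2 secretion in vitro". Each is given with alpha = 5% and beta = 7.5%, "in a two tailed test based upon after 30 days supplementation". Objectives 3 and 4 concern Camelina versus fish oil after 8 weeks.

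**The concern.** A claim that two treatments are comparable needs a statement of how large a difference would still count as comparable, and a rule for setting the estimate and its uncertainty against that limit. The plan has neither. A non-significant treatment effect may only reflect imprecision. A significant one may be too small to matter. The label could therefore be chosen after the results are seen.

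The Study B power statements do not fill the gap. An increase could be over baseline, over fish oil or over something else, and the plan does not say which. The figures cannot be read as assurance about the planned 8-week comparison of the oils.

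**Working it through.** **1. Aim against plan.** The aim is comparability. Sections 9, 11 and 12 offer ANOVA, an unspecified comparison, and ANCOVA. No section gives a limit, a confidence-interval rule or a definition of comparable.

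**2. Stated power against beta.** Power = 1 − beta = 1 − 0.075 = 92.5%.

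| Section 12 statement | Stated power | Beta | 1 − beta |
|---|---|---|---|
| Study A, TAG EPA or DHA, 10% | 85% | 7.5% | 92.5% |
| Study A, VLDL concentration and size | 85% | 7.5% | 92.5% |
| Study A, IL-6, 30% | 80% | 20% | 80% |
| Study B, phospholipid EPA or DHA, 40% | 80% | 7.5% | 92.5% |
| Study B, IL-4 and IL-2, 10% | 85% | 7.5% | 92.5% |

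Only the IL-6 statement agrees with itself. Ten per group cannot be reproduced for any line, because no SD is given.

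**3. Illustration for the 40% phospholipid line.** Inputs from the plan are n = 10, two-sided 5%, 80% power, a 40% effect, and 4 age-by-sex cells × 10 = 40 subjects. The assumptions are mine: all 40 complete, the phases are pooled, and r is the correlation between a subject's results on the two oils.

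- The standardised effect that n = 10 detects with 80% power (non-central t) is 1.325 two-sample or 0.996 paired.
- Implied SD: 40/1.325 = 30.2 or 40/0.996 = 40.2 points.
- Between-oil SD = implied SD × √(2(1 − r)). At r = 0.5 the factor is 1. In the paired reading the SD is taken as that of the change on one oil, and r correlates the two changes.
- SE = SD/√40 = 4.77 or 6.35, with 38 df.
- 90% CI half-width = 1.686 × SE = 8.0 or 10.7.
- A true 10-point gap has non-centrality 10/4.77 = 2.09 or 10/6.35 = 1.57, and is non-significant in 46.7% or 66.4% of trials. Over r = 0.8 to r = 0 the range is 10% to 81%.
- If beta = 7.5% was what the authors meant, the r = 0.5 figures become 30% to 54%, with half-width 7 to 9.

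**4. If the phases are not pooled.** Assume first-phase data only, 20 v 20, SD 30. SE = 30 × √(2/20) = 9.49. The gap detectable with 80% power is 2.875 × 9.49 ≈ 27 points, and the 90% half-width is 1.686 × 9.49 ≈ 16.

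**5. The IL-4/IL-2 line by the same method.** At 85% power the standardised effects are 1.417 and 1.066, so SD = 10/1.417 = 7.06 or 10/1.066 = 9.38. The detectable gap with 40 pooled subjects at r = 0.5 is 2.875/√40 × SD = 0.4546 × SD = 3.2% or 4.3%. The phospholipid figures do not carry over to this outcome.

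**6. What an interval rule would deliver for phospholipids.** Take an assumed 10-point limit, two one-sided tests (90% CI inside the limit), 40 pooled subjects and the 80% reading. At r = 0.5, power is 32% or 3% if the oils are truly equal. The 32% falls to about 20% if the true difference is 5 points. At r = 0 it is about 1% or less; at r = 0.8, with equal oils, it is 58% to 89%. If beta = 7.5% was meant, the best case at r = 0.5 with equal oils is 61%.

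**The case against.** The strongest reply is that this is a mechanistic study in healthy volunteers. The word comparable appears in one broad aim sentence, the objectives are about measuring, and the planned models estimate the between-oil difference those objectives need. That stands, and it lowers the severity. It does not remove the gap, because the headline aim is framed as a test and no test of comparability is defined.

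A reader might go further in four ways that the documents do not support:

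- **That the plan will report p>0.05 as comparability.** No section says so. The harm is a label that could be chosen afterwards, not a planned wrong inference.
- **That both studies are too small.** Study A is not shown to be: if 10% were the limit, 40 pooled subjects would give over 99% power with truly equal oils for every implied SD. For Study B the answer depends on an unstated limit and SD.
- **That the 10% in Study A or the 40% in Study B is an implicit comparability limit.** Each is described only as detectable. The sponsor would have to justify either one as a limit.
- **That Study B's immune outcomes fare worst.** For IL-4 and IL-2 the plan's own figures imply a small detectable gap.

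It is also fair to say that the illustration rests on invented correlations and on SDs from cited work not reproduced in the plan. A 10% to 81% range shows dependence on unstated inputs; it does not measure the harm. A symmetric limit could also fail an oil that is better, which matters because the background allows for that.

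**Conclusion.** The point holds and should be fixed before unblinding. The plan cannot answer its own overall aim as written, although it can meet its measurement objectives. Study B's two power statements are not stated as power for the 8-week comparison of the oils. The power and beta figures conflict in four of five statements. These three conclusions rest on the text alone.

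The size is illustrative. It rests on SDs back-solved from the 40% line, 40 completers, pooled phases, an assumed r, and a 10-point gap chosen for illustration. It applies to Study B phospholipid EPA or DHA only.

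**What to change.** Before unblinding:

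- (a) Name one main EPA/DHA outcome for each study.
- (b) Pre-specify and justify a comparability limit for it. Judge it by the confidence interval of the Camelina/fish-oil difference or ratio, from a model that respects the crossover. Use a two-sided rule (90% CI), or a one-sided non-inferiority rule if a better Camelina result should still count as success.
- (c) State that p>0.05 alone will not be reported as comparability, nor p<0.05 alone as lack of it. Keep the two-tailed test for whether Camelina oil is more efficacious.
- (d) State the comparator and time point of Study B's 40% and 10% figures, and what ten per group means in a crossover with four age-by-sex cells. Restate the expected between-oil precision with and without pooling of phases.
- (e) Reconcile stated power with beta throughout section 12.

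The cost is plan wording and a restated power section, with no new subjects, visits or assays. The downside is that Study B phospholipid outcomes may have to be reported as inconclusive under a tight limit, as may outcomes with no power statement.
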